4.1 Inclusion Criteria

- 4.1.1 Age 18 or older
- 4.1.2 Clinical history of advanced CKD not on dialysis with at least 1 historic estimated glomerular filtration rate (eGFR) < 45.0 mL/min/1.73m² at least 12 weeks prior to screening
- 4.1.3 **Not currently receiving dialysis with an** eGFR < 45.0 mL/min/1.73m², per the central laboratory during screening
- 4.1.4 Chronic anemia due to renal failure
- 4.1.5 Two Hb concentrations < 10.0 g/dL, at least 2 weeks apart during screening using the **modified** Hb point of care (POC) device

- 4.1.6 Iron replete, defined as a transferrin saturation (TSAT) \geq 20% and a ferritin \geq 100 ng/mL, per the central laboratory during screening
- 4.1.7 Vitamin B12 and folate replete, defined as a vitamin B12 level $>$ 180 pg/mL and a folate concentration $>$ 7 nmol/L, per the central laboratory during screening
- 4.1.8 Clinically stable in the opinion of the investigator
- 4.1.9 Subject has provided written informed consent

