7.1.3 Study Day 1 Evaluations

The Day 1 visit will be the same day as screening Visit 2. After completion of the screening period, when the subject has met all eligibility criteria, sites will need to complete the randomization call in the IVR/IWR system prior to beginning the Day 1 evaluations. All subsequent doses and study visits will be scheduled based on the Day 1 date.

The following procedures will be completed on Day 1:

- Medical and surgical history, including history of transfusions
- Physical exam, including height and weight
- Electrocardiogram
- Concomitant medications (as specified in [Section 7.2.9](#))
- eGFR, serum creatinine
- Complete blood count (CBC; results will remain blinded)
- TSAT, ferritin, iron, TIBC
- Troponin-T
- Serum albumin, high sensitivity C-reactive protein (CRP)
- Reticulocytes (results will remain blinded)
- Blood samples for biomarkers
- Spot urine albumin and creatinine
- Anti-erythropoietic protein antibodies
- Anti-human leukocyte antigen (HLA) antibodies
- Investigational product administered

Once the subject is enrolled, collection of the following will begin:

- RBC transfusions, as well as transfusions of other blood-derived products
- Endpoint data for adjudication
- Hospitalizations, including observational stays, and emergency department visits
- Adverse events

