14. APPENDICES

Appendix A. Schedule of Assessments

Treatments and Procedures	Screening		Visit Frequency						
	Visit 1	Visit 2 (g)	Day 1	Week 5	Q4W	Q2W (i)	Q12W	Q24W	EOS/ET Week 101
General and Safety Assessments									
Informed consent (a)	X								
Medical/surgical history , including history of transfusions			X						
Physical exam and height (b)			X						X
Electrocardiogram			X						
Blood pressure, pulse	X	X	X	X	X	X			X
Weight	X		X						X
Concomitant medications including iron, and commercial ESAs			X	X	X				X
Concomitant medications – antihypertensive medications			X	X	X	X			X
RBC transfusions and transfusions of other blood-derived products (c)									Record continuously
Endpoint data collection for adjudication (c)									Record continuously
Hospitalizations, including observational stays, and emergency department visits (c)									Record continuously
Adverse events/serious adverse events (d, e)									Record continuously
Laboratory Assessments (f)									
eGFR, serum creatinine (h)	X		X						X
Complete blood count (CBC)			X	X				X	
Hb, using modified Hb point of care device	X	X	X	X					X
TSAT, ferritin, iron, TIBC	X		X	X				X	
Vitamin B12, folate	X								
Serum pregnancy test (all women of child bearing potential)	X								
Blood samples for biomarkers			X					X	X
Anti-HLA antibodies			X				X		X
Spot urine albumin and creatinine			X						
Troponin-T, serum albumin, high sensitivity CRP			X						
Reticulocytes			X						
Anti-erythropoietic protein antibodies			X						X
Dosing									
Investigational product administration			X	X	X				

a) To occur before any study procedure
 b) Rectal and gynecological not required
 c) Record continuously throughout duration of study
 d) Serious adverse events collected from date of consent through 4 weeks after final dose of IP (see [Section 9.2.2](#) for) additional details
 Adverse events, collected from Day 1 through 4 weeks after final dose of IP

f) Samples should be drawn before investigational product administration
 g) Eligible subjects must have Visit 2 and Day 1 completed on the same date
 h) eGFR and serum creatinine will not be performed on subjects who require renal replacement therapy
 i) Required if SBP \geq 160 mmHg during routine study visit, at investigator discretion if SBP < 160 mmHg

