Defined as the number and percentage of subjects with a reported event(s). For subjects with multiple reports of the same event during the study, the subject will be counted only once. If a pre-existing condition worsens on or after the first dose of investigational product administered, the event will be counted as if it occurred on the day it worsened. For adverse event tabulations involving relationship to investigational product, the subject is counted in the tabulations if at least 1 occurrence of the event is

related. For adverse event tabulations involving severity, the highest severity of the particular adverse event will be used for each subject.

Hemoglobin

For all Hb-related endpoints, the Hb measured using the point of care device will be used. For Hb measured by the central laboratory, they will only be summarized descriptively by treatment group at each scheduled visit.

Achieved Hb Concentration while Receiving Investigational Product

For each subject, the achieved Hb concentration while receiving IP will be derived using the area under the curve (AUC) method with all Hb measured during the period starting from Week 13 (Study Day 85) to the last dose date will be included in the calculation. The 12 week interval is indicated in the USPI as escalation period.

Post-baseline Hb Concentration Subgroup

Post-baseline Hb concentration subgroup is defined as < 8.0, ≥ 8.0 and < 9.0, ≥ 9.0 and < 9.5, ≥ 9.5 and < 10.0, ≥ 10.0 and ≤ 10.5, > 10.5 and ≤ 11.0, > 11.0 and ≤ 12.0, > 12.0 and ≤ 13.0, > 13.0 g/dL

Hb Rate of Change (ROC)

Only Hb measured on and after Study Day 1 and while the subject is receiving the investigational product will be included in the calculation.

ROC (g/dL per 4 weeks) is calculated using the following equation:

$$\text{ROC (g/dL/4weeks)} = [(\text{Hb at visit X} - \text{Hb at Visit Y}) / (\text{Date of Visit X} - \text{Date of Visit Y})] * 28, \text{ where X and Y are consecutive post-baseline visits.}$$

Time to Reach Hb ≥ 10.0 g/dL

Time from the Study Day 1 to the date the Hb measurement reached ≥ 10.0 g/dL for the first time. Subjects who never reach Hb ≥ 10.0 g/dL will be censored on the last date of IP.

Proportion of Hb measurements ≥ 10.0 g/dL

Proportion of Hb measurements ≥ 10.0 g/dL = the number of Hb measurements ≥ 10.0 g/dL / Total number of Hb measurements. Only Hb measured on or after Study Day 1 and while the subject is receiving the investigational product will be included in the calculation.

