10.5.3 Analyses of Exploratory Endpoints

The following exploratory endpoints will be summarized by each treatment group using the full analysis set:

- Darbepoetin alfa dose and weight-adjusted dose received at each study visit
- Hb concentration and its subgroup at each study visit
- Hb concentration change from baseline at each study visit
- Time to first Hb concentration ≥ 10.0 g/dL
- Proportion of Hb measurements ≥ 10.0 g/dL
- Hb rate of change in a 4 week interval at each study visit
- Hb variability at each study visit
- Anti-HLA antibodies as measured using panel reacted antibodies (PRA) over time based on both on-treatment and on-study approaches

Anti-HLA antibodies over time will be summarized by the transfusion subgroup (on-treatment approach) and by randomized treatment group using the full analysis set. The summary will be repeated by the transfusion subgroup (on-study approach) and by randomized treatment group using all randomized subjects.

Furthermore, the following Hb-related information will be evaluated and summarized by randomized treatment group using the full analysis set

- At least one Hb < 8.0 g/dL and the proportion of the Hb measurements < 8.0 g/dL
- At least one Hb < 9.0 g/dL and the proportion of the Hb measurements < 9.0 g/dL
- At least one Hb > 11.0 g/dL and the proportion of the Hb measurements > 11.0 g/dL
- At least one Hb > 12.0 g/dL and the proportion of the Hb measurements > 12.0 g/dL
- At least one Hb > 13.0 g/dL and the proportion of the Hb measurements > 13.0 g/dL

Number of days hospitalized will be summarized by treatment group using the on-treatment approach and the full analysis set. As a sensitivity analysis, the number of days hospitalized will also be summarized by treatment group using the on-study approach and all randomized subjects.

Initial Hb response at Week 5 will be summarized by treatment group using initial Hb response analysis set. The following will be summarized by initial Hb-response subgroup and treatment group using the initial Hb response analysis set:

- Hb concentration at each study visit and the achieved Hb
- Darbepoetin alfa dose at each study visit and the cumulative dose

Subjects received ≥ 1 RBC transfusion and time to first RBC transfusion will be descriptively summarized by the initial Hb response subgroup using on-treatment approach.

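### The proportion of Hb values at or above 10.0 g/dL counts the pre-dose Day 1 value, which the entry criterion holds below 10.0, so the exploratory endpoint is understated

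*SAP*

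**What the plan says.** SAP 6.3 gives the endpoint as "the number of Hb measurements ≥ 10.0 g/dL / Total number of Hb measurements", restricted by date and treatment status: "Only Hb measured on or after Study Day 1 and while the subject is receiving the investigational product will be included in the calculation". The same section fixes the source of the values: "For all Hb-related endpoints, the Hb measured using the point of care device will be used". SAP 6.1 sets Study Day 1 as the day of randomization, on which the first dose must be given.

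The protocol settles what the Day 1 value is. Section 7.1.3 states "The Day 1 visit will be the same day as screening Visit 2", and a footnote to the Schedule of Assessments (Appendix A) repeats it: "Eligible subjects must have Visit 2 and Day 1 completed on the same date". Section 7.1.1 lists a point-of-care Hb at screening Visit 2. Criterion 4.1.5 requires "Two Hb concentrations < 10.0 g/dL, at least 2 weeks apart during screening", measured on that same device. Section 7.2.5 has Hb drawn before the dose on the day of each visit.

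Two other definitions in SAP 6.3 avoid the problem or limit it. Average achieved Hb starts at Week 13. The rate-of-change formula names consecutive post-baseline visits.

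**The concern.** A measure of how often Hb reaches 10.0 g/dL on treatment should count only values that treatment could have influenced. The Day 1 value is a screening value: it precedes any drug, and a subject who enters under the criteria has it below 10.0. SAP 6.2 also defines baseline Hb as the mean of the two most recent values up to and including the randomization date. The same reading is therefore normally half of the baseline and also one of the on-treatment results.

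Holding Hb at or above 10.0 g/dL is the stated aim of the titration arm (Protocol 3.1), so this endpoint describes attainment of that aim. Protocol 2.3 lists Hb-related parameters among the considerations for choosing a preferred regimen. A built-in shortfall that is larger, in relative terms, for subjects with few measurements makes the endpoint harder to read.

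**Working it through.** The documents give no planned or expected figure for this endpoint, so there is none to reproduce.

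**Inputs from the documents.** Visits run every 4 weeks from Week 5 to Week 97 (Protocol 7.1.4.1). That is (97 − 5)/4 + 1 = 24 post-dose values for a completer, or 25 values with Day 1. If the Week 101 value also counted, there would be 25 post-dose values.

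**Assumed inputs.** The share q of post-dose values at or above 10.0 g/dL, and the fraction and timing of early stopping, are not in the documents. They are varied below.

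**Formula.** With k post-dose values and one forced failure on Day 1, the subject's result is q×k/(k+1). The relative loss is 1/(k+1) and the absolute shift is −q/(k+1).

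| k | Ceiling k/(k+1) | Result when q = 0.60 | Shift (points) |
|---|---|---|---|
| 24 | 96% | 0.576 | −2.4 |
| 12 | 92.3% | 0.554 | −4.6 |
| 6 | 85.7% | 0.514 | −8.6 |
| 3 | 75% | 0.450 | −15.0 |
| 1 | 50% | 0.300 | −30.0 |

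With k = 0 the subject scores 0% instead of having no evaluable result. Counting Week 101 moves a completer's ceiling only to 25/26 = 96.2%.

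**Average over an arm, per-subject averaging.** Assume q is unrelated to k and early stoppers are spread evenly over k = 1 to 23. Their mean relative loss is (1/2 + 1/3 + … + 1/24)/23 = 2.776/23 = 12.1%. A completer's is 1/25 = 4%.
- 20% stop early: 0.8 × 4% + 0.2 × 12.1% = 5.6%.
- 40% stop early: 0.6 × 4% + 0.4 × 12.1% = 7.2%.

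**Between arms, q = 0.60 in both.**
- Everyone completes: a true gap of 10 points is reported as 10 × 24/25 = 9.6.
- Evenly spread stopping, 20% in one arm and 40% in the other: the spurious gap is 0.60 × (7.2% − 5.6%), about 1 point.
- Harsher case, with all early stoppers leaving after three post-dose values: 0.8 × 0.576 + 0.2 × 0.450 = 0.551, against 0.6 × 0.576 + 0.4 × 0.450 = 0.526. The spurious gap is 2.5 points. It ranges from 0.8 to 7.4 points over q of 0.4 to 0.8 and k of 1 to 6.

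**If measurements are pooled instead.** With q = 0.60 and stoppers at k = 3, the pooled proportion is [(1 − s)×24×0.60 + s×3×0.60] / [(1 − s)×25 + s×4] for early-stopping fraction s. This gives 0.576, 0.571 and 0.564 at s = 0, 20% and 40%. The gap between 20% and 40% falls from 2.5 to about 0.7 points.

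**The case against.** **The wording may already exclude the value.** The sentence also requires that the subject be receiving investigational product, and the Day 1 sample precedes any dose. Protocol 7.1.3 does not list point-of-care Hb among the Day 1 procedures; it belongs to screening Visit 2. The phrase could be a stock date filter, since the adjacent rate-of-change definition uses nearly the same words. This has some force as a guess at intent. As a rule for a programmer it does not succeed: the sentence names Study Day 1 as included, SAP 6.3 counts exposure from the first dose date, and SAP Appendix A gives point-of-care Hb a Week 1 window centred on day 1. If the intent was to exclude the value, the same edit is needed.

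**The effect may be equal in both arms.** A reader might infer that the arms are diluted unequally. The documents do not support that as a fact. Both arms share the visit schedule and starting dose, and nothing gives or predicts discontinuation by arm. The protocol does plan sensitivity analyses of the primary endpoint for differential follow-up (10.5.2.1), and it lists lack of efficacy as a reason to stop product (8.1). Unequal dilution is therefore possible, but not shown.

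**Early stoppers do not always lose more.** This stands for absolute points. A stopper with q = 0 loses nothing. One with q = 0.10 and k = 3 loses 0.10/4 = 2.5 points, less than a completer with q = 0.80, who loses 0.80/25 = 3.2. Only the relative loss always rises as k falls.

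**Little rides on it.** This also stands. The endpoint is exploratory and descriptive, no hypothesis is tested, and Hb is also tabulated visit by visit.

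**Conclusion.** The point holds: the rule as written gives a wrong result, though a minor one. Each subject enrolled under the Hb criterion contributes one guaranteed value below 10.0 g/dL. Only a subject randomized in deviation from that criterion could escape this. For completers the loss is 4% in relative terms and at most 4 percentage points.

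The arm-level losses of 5.6% and 7.2% rest on per-subject averaging, evenly spread stopping and q unrelated to k. The SAP does not say whether the proportion is averaged per subject or pooled, and pooling greatly reduces the early-stopper effect. A spurious difference between arms requires different discontinuation, or different numbers of values, by arm. With equal discontinuation, a true difference is only slightly attenuated.

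A reader might also infer that the other Hb threshold summaries in SAP 10.5.3, such as "At least one Hb < 9.0 g/dL and the proportion of the Hb measurements < 9.0 g/dL", are affected. That section states no start point, and the general rule in SAP 10.1 limits Hb summaries to measurements taken on product without naming Day 1. For those summaries the documents show a gap, not an error. If Day 1 were counted, a subject with a Day 1 value below 9.0 would meet the at-least-one criterion before any drug.

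The primary analysis is unaffected, and so are the secondary ones; average achieved Hb starts at Week 13.

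**What to change.** In SAP 6.3, for this endpoint, replace the inclusive Day 1 start with *after Study Day 1 (from the Week 5 visit)*. Treat subjects with no post-dose Hb as non-evaluable and report their number by arm, so that they do not score 0%. State whether the proportion is computed per subject and then averaged, or pooled over measurements.

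For consistency, state the same post-dose window for the < 8.0, < 9.0, > 11.0, > 12.0 and > 13.0 g/dL summaries in SAP 10.5.3. For the three upper thresholds a Day 1 value below 10.0 could dilute only the proportions; it could not trigger the at-least-one counts.

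The cost is a few words in the SAP and one extra count in the tables. No data collection changes. The denominator will be smaller by the subjects who have no post-dose value, and reporting their number covers that.

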5.2 Randomization

Randomization by the IVR/IWR system will be done in a 1:1 ratio to 1 of the 2 treatment groups (Hb-based titration group or fixed dose group) based on the following stratification factors at the time of study entry:

- Receipt of any RBC transfusion within the 12 months prior to randomization (yes/no)
- Site practice setting (nephrology/non-nephrology), pre-specified by the specialty of the principal investigator at the time of site initiation

Randomization will be based on a schedule generated before the start of the study by an Amgen representative not involved in the conduct of the study.

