6.3 Other Study Related Definitions

Analytical Window Assignments

Analytical windows will be used to summarize protocol specified parameters according to the protocol schedule. This algorithm is provided in [Appendix A](#).

Analytical Window Assignments

Analytical windows will be used to summarize protocol specified parameters according to the protocol schedule.

Exposure to Investigational Product

For each subject who received at least one dose of IP, the number of days of IP exposure Period is calculated as [(Date of Last Dose of Investigational Product Received – first dose date + 1) + 28 days]. The exposure to IP in study month = exposure to IP / 28 days.

Study Exposure

For each randomized subject, study exposure is defined as time from the randomization date to the end of study date.

Evaluation Periods for Different Analysis Approaches

The evaluation period of the on-treatment approach begins from the date of randomization, and subjects will be censored at the last dose of investigational product plus 3 months or end of study, whichever is earlier.

The evaluation period of the on-study approach begins at the date of randomization and subjects will be censored at the end of study date.

Treatment Emergent Adverse Events

Treatment emergent adverse events are adverse events occurring on or after the first dose of IP.

Adverse Events of Special Interest

Adverse events falling into categories of special interest (EOI) will be reported according to the special interest category. The categories of interest for the study are:

- Hypertension
- Ischemic Heart Disease
- Cardiac Failure
- Cerebrovascular Disorders
- Dialysis Vascular Access Thrombosis
- Embolic and Thrombotic Events (including arterial thromboembolic events, venous thromboembolic events and vessel type unspecified and mixed arterial and venous)
- Convulsions
- Antibody-Mediated Pure Red Cell Aplasia (PRCA)
- Hypersensitivity
- Lack of Efficacy-Effect
- Malignancies

The definition of each EOI may be modified and a new EOI may be added based on findings from ongoing pharmacovigilance. Updates of the search strategy due to MedDRA upgrades or other reasons may not trigger a SAP amendment. However, the most recent EOIs per Amgen EOI search strategy will be used at the time of the analysis and these search terms will be included in an appendix of the study report.

Adverse Event Subject Incidence

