Hb variability

At any study visit, the Hb variability is the intra-subject Hb standard deviation over the prior 6 months. The Hb variability will be calculated at each scheduled visit from Week 25.

Initial Hb Response

Initial Hb response is defined as the change of Hb concentration from baseline at Week 5.

Initial Hb Response Subgroup

Initial Hb response subgroups are defined as the initial Hb response quartiles based on the initial Hb response analysis set subjects ([Section 7.3](#)) from both treatment groups.

Dose

The dose referred in this analysis plan is the darbepoetin alfa dose from the IP administration. The dose from a placebo injection equals zero darbepoetin alfa dose.

Weight-based Dose at Specific Study Visit

The weight-based dose at any time point = Dose in μg at specific study visit / subject's screening weight in kg.

Cumulative Dose at Specific Study Visit

The cumulative dose at specific study visit = sum of all darbepoetin alfa doses received from Study Day 1 through the specific study visit.

Average Cumulative Dose per 4 Week at Specific Study Visit

Average cumulative dose per 4 week at specific study visit is defined as the 4-week equivalent cumulative dose received at specific study visit.

Average Cumulative Weight-adjusted Dose per 4 Week at Specific Study Visit

Average cumulative weight-adjusted dose per 4 week at specific study visit = average cumulative dose per 4 week at specific study visit / the screening weight in kg.

Transfusion Subgroups

Subjects will be categorized into transfusion subgroups based on the number of transfusion events: No transfusion event, one transfusion event, more than 1 transfusion event.

Transfusion subgroup (on-treatment approach) will be defined using the number of transfusion events where the start date of the transfusion event falls within the evaluation period of the on-treatment approach.

Transfusion subgroup (on-study approach) will be defined using the number of transfusion events where the start date of the transfusion event falls within the evaluation period of the on-study approach.

Time to Event Derivation

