	Darbepoetin alfa Dose Received at Each Study Visit – <<Full Analysis Set>>	Summary of the darbepoetin alfa dose received at each study visit by treatment group.
	Darbepoetin alfa Weight-adjusted Dose Received at Each Study Visit – <<Full Analysis Set>>	Summary of the darbepoetin alfa weight-adjusted dose received at each study visit by treatment group.
	Hb Concentration at Each Study Visit – <<Full Analysis Set>>	Summarize the Hb concentration and its subgroup at each study visit by treatment group.
	Hb Concentration Change from Baseline at Each Study Visit – <<Full Analysis Set>>	Summarize the Hb concentration change from baseline at each study visit by treatment group.
	Time to First Hb Concentration ≥ 10.0 g/dL – <<Full Analysis Set>>	Summary of the time to first Hb concentration ≥ 10.0 g/dL by treatment group.
	Proportion of Hb Measurements ≥ 10.0 g/dL – <<Full Analysis Set>>	Summarize the proportion of Hb measurements ≥ 10.0 g/dL by treatment group in the <<Full Analysis Set>>.
	Hb Rate of Change in a 4 Week Interval at Each Study Visit – <<Full Analysis Set>>	Summary the Hb rate of change in a 4 week interval at each study visit by treatment group.
	Hb Variability at Each Study Visit – <<Full Analysis Set>>	Summary of the Hb variability at each study visit by treatment group.
	Anti-human Leukocyte Antigen (HLA) Antibodies over Time – <<Full Analysis Set>>	Summarize the anti-human leukocyte antigen (HLA) antibodies over time by treatment group using on-treatment approach.
	Anti-human Leukocyte Antigen (HLA) Antibodies over Time – <<All Randomized Subjects>>	Summarize the anti-human leukocyte antigen (HLA) antibodies over time by treatment group using on-study approach.
	Anti-human Leukocyte Antigen (HLA) Antibodies over Time by Transfusion Subgroup – <<Full Analysis Set>>	Summarize the anti-human leukocyte antigen (HLA) antibodies over time by transfusion subgroup and treatment group using on-treatment approach.
	Anti-human Leukocyte Antigen (HLA) Antibodies over Time by Transfusion Subgroup – << All Randomized Subjects >>	Summarize the anti-human leukocyte antigen (HLA) antibodies over time by transfusion subgroup and treatment group using on-study approach.

Category	Data/ Endpoint	Description

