Week 85	589	575 ≤ Study days ≤ 602
Week 89	617	603 ≤ Study days ≤ 630
Week 93	645	631 ≤ Study days ≤ 658
Week 97	673	659 ≤ Study days ≤ 686
Week 101	701	687 ≤ Study days

- For protocol-specified study assessment occurred at Day 1, Weeks 5, 13 and every 12 weeks (CBC, TSAT, ferritin, iron, TIBC), the analytical windows are:

Scheduled Visit	Planned Study day	Analytical Study Days
Week 1	1	1 ≤ Study days ≤ 14
Week 5	29	15 ≤ Study days ≤ 57
Week 13	85	57 ≤ Study days ≤ 126
Week 25	169	127 ≤ Study days ≤ 210
Week 37	253	211 ≤ Study days ≤ 294
Week 49	337	295 ≤ Study days ≤ 378
Week 61	421	379 ≤ Study days ≤ 462
Week 73	505	463 ≤ Study days ≤ 546
Week 85	589	547 ≤ Study days ≤ 630
Week 97	673	631 ≤ Study days

- For protocol-specified study assessment occurred at Day 1, Week 25 and every 24 weeks afterwards (eGFR and serum creatinine), the analytical windows are:

[figure not shown]
Scheduled Visit	Planned Study day	Analytical Study Days
Week 1	1	1 ≤ Study days ≤ 85
Week 25	169	86 ≤ Study days ≤ 252
Week 49	337	253 ≤ Study days ≤ 420
Week 73	505	421 ≤ Study days ≤ 588
Week 97	673	589 ≤ Study days ≤ 686
Week 101	701	687 ≤ Study days

- For protocol-specified study assessment occurred at Day 1, Week 13 and every 12 weeks afterwards (Anti-HLA antibodies), the analytical windows are:

Scheduled Visit	Planned Study day	Analytical Study Days
Week 1	1	1 ≤ Study days ≤ 43
Week 13	85	44 ≤ Study days ≤ 126
Week 25	169	127 ≤ Study days ≤ 210
Week 37	253	211 ≤ Study days ≤ 294
Week 49	337	295 ≤ Study days ≤ 378
Week 61	421	379 ≤ Study days ≤ 462
Week 73	505	463 ≤ Study days ≤ 546
Week 85	589	547 ≤ Study days ≤ 630
Week 97	673	631 ≤ Study days

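### The anti-HLA table by transfusion subgroup counts transfusions given after the sample, so its post-baseline columns before Week 97 do not show antibody status after transfusion

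*SAP*

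**What the plan says.** SAP 6.3, under Transfusion Subgroups, sets three levels: "No transfusion event, one transfusion event, more than 1 transfusion event". For the on-treatment version a subject's level comes from the "number of transfusion events where the start date of the transfusion event falls within the evaluation period of the on-treatment approach". For the on-study version it comes from the "number of transfusion events where the start date of the transfusion event falls within the evaluation period of the on-study approach". Both periods start at randomization. The on-study period runs to the end of study. In the on-treatment period "subjects will be censored at the last dose of investigational product plus 3 months or end of study, whichever is earlier", and the SAP takes 3 months as 84 days.

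SAP 10.5.3 applies the subgroup to a longitudinal outcome: "Anti-HLA antibodies over time will be summarized by the transfusion subgroup (on-treatment approach) and by randomized treatment group using the full analysis set". It repeats the summary on-study with all randomized subjects. SAP 12.1 lists both tables.

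Protocol 7.1.3 and 7.1.4.1 and SAP Appendix A put anti-HLA sampling at Day 1 and then every 12 weeks from Week 13 to Week 97. Protocol 7.1.7 adds a sample at the end-of-study or early-termination visit.

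No section ties the transfusion count to the sample date, and none adds a landmark or before-and-after analysis. By contrast, two other definitions in SAP 6.3 look only backward from the visit: cumulative dose sums doses from Day 1 up to that visit, and Hb variability uses the preceding 6 months.

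**The concern.** The subgroup is fixed by what happens over the whole evaluation period, but it labels antibody results at each visit within that period. At a given post-baseline visit, the 'one' and 'more than one' rows therefore mix samples taken after a transfusion with samples taken before it. The 'none' row contains no later-transfused subjects, but it is selected on the future, and subjects with short follow-up have less chance of leaving it.

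Allosensitization over time is a stated exploratory objective, and Protocol 2.1 names it as a risk of transfusion. These are the only planned tables that relate the antibodies to transfusion, so a reader will naturally take a row as status after that many transfusions.

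If later-transfused and never-transfused subjects have the same positivity before transfusion, the difference between rows is diluted, most of all at early visits. If they differ beforehand, selection can move it either way. That is plausible here, because subjects transfused in the 12 months before randomization are enrolled and form a randomization stratum (Protocol 5.2).

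**Working it through.** **The plan's own figure.** The documents give no number for this table. The 25% used below comes from the sample-size section (SAP 3.2), which reproduces: 300/(1 − 0.20) = 375 per group. The 95% CI width at n = 300 is 2 × 1.96 × √(0.25 × 0.75/300) = 9.8%, within the stated 10%. The width for the difference is 2 × 1.96 × √(2 × 0.25 × 0.75/300) = 13.9%, within the stated 14%.

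**Inputs.** From the documents: 25% transfused at least once, 100 weeks on study (Protocol 3.4.1), 375 per arm and the sampling weeks. Assumed: the timing of transfusions. A visit at Week w is taken as t = w − 1 elapsed weeks.

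**Share of ever-transfused subjects with no transfusion yet.** With cumulative hazard L(t) and L(100) = −ln(0.75) = 0.2877,

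share(t) = 1 − [1 − exp(−L(t))]/0.25.

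- Constant hazard: L(t) = 0.2877 × t/100. At Week 49, L(48) = 0.1381 and 1 − exp(−0.1381) = 0.1290, so the share is 1 − 0.1290/0.25 = 48%.
- Threefold hazard in weeks 0 to 12: L(100) = (36 + 88)h = 124h, so h = 0.00232. At Week 13, L(12) = 36h = 0.0835 and 1 − exp(−0.0835) = 0.0801, so the share is 1 − 0.0801/0.25 = 68%.

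**By planned row.** With independent events at a constant rate, the single event in the 'one' row is uniform over the 100 weeks, so the share not yet transfused is 1 − t/100. For the 'more than one' row two Poisson quantities matter: no event yet, and fewer than two events so far. The second includes subjects already exposed once.

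| Week | Pooled, constant | Pooled, early threefold | 'One': none yet | 'More than one': none yet | 'More than one': fewer than 2 |
|---|---|---|---|---|---|
| 13 | 86% | 68% | 88% | 77% | 98% |
| 25 | 73% | 58% | 76% | 56% | 93% |
| 37 | 61% | 48% | 64% | 40% | 85% |
| 49 | 48% | 38% | 52% | 26% | 75% |
| 61 | 37% | 29% | 40% | 15% | 61% |
| 73 | 25% | 20% | 28% | 7% | 45% |
| 85 | 14% | 11% | 16% | 2% | 27% |
| 97 | 3.5% | 3% | 4% | 0.1% | 7% |

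**Sensitivity.** At Week 49 the pooled share is 47% to 50% for 35% down to 15% transfused. It is 28% to 64% for Weibull timing with shape 0.5 (early-loaded) to 1.5 (late-loaded). It is 35% to 41% if proneness to transfusion varies between subjects as a gamma frailty with shape 0.25 to 0.5. If 50% stop investigational product by Week 100 (exponential), with the on-treatment period ending 12 weeks after stopping, the pooled share among subjects still in evaluation is 83% at Week 13, 44% at Week 49 and 3% at Week 97.

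**Effect on the displayed curve.** Suppose positivity rises by an assumed 10 points immediately after a transfusion and stays there, and the rows are otherwise alike. The 'one' row then shows an excess of 10 × t/100 points: 1.2 at Week 13, 4.8 at Week 49, 8.4 at Week 85 and 9.6 at Week 97. The gradual climb is only transfusions accruing.

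**The case against.** The plan never says that a visit column is to be read as antibody status after 0, 1 or more transfusions. The objective is to describe allosensitization by dosing strategy, and the by-arm summary does that. A fixed-cohort display is legitimate: it follows the same people from Day 1 and shows whether the eventual groups already differed at baseline. A time-updated grouping changes membership at every visit, has few exposed subjects early on, and so mixes composition with antibody change. The shares above measure misclassification, not bias in positivity, because the documents give neither transfusion timing nor antibody prevalence. A time-updated 'none' group would still contain subjects transfused in the year before randomization.

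Most of this stands as a limit on importance. The fixed display is worth keeping, the effect on reported positivity cannot be computed, and the time-updated table will not be a clean causal contrast. It does not remove the problem. The SAP does not label the table as a fixed-cohort view, and it offers no other table that relates antibodies to transfusions already received. The fewer-than-two series must also be read as misplacement in the dose category, not as absence of exposure. The end-of-study sample is essentially unaffected.

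**Conclusion.** The concern holds, as a minor point. The definition, its use in an over-time table and the absence of any time-updated alternative are all clear in the SAP, so the mixing is there whatever the timing of transfusions. Its size depends on assumed timing. With 25% transfused, not-yet-transfused subjects are the majority of the pooled transfused rows up to Week 37 at constant hazard, or up to Week 25 with a threefold early hazard. By Week 97 they are about 3% to 4%. The Day 1 column remains a valid baseline comparison of the eventual groups.

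The consequence is confined to the by-transfusion anti-HLA table and its on-study repeat, both exploratory and descriptive. The primary endpoint, sample size and by-arm anti-HLA summaries are not affected.

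**What to change.** Change the Transfusion Subgroups definition in SAP 6.3 so that each post-baseline anti-HLA sample is classified by the number of transfusion events (0, 1, more than 1) that started on or after randomization and before that sample's date. Apply it to both the on-treatment and on-study tables in SAP 10.5.3 and 12.1. Keep the whole-period grouping only as a supplement, labelled as trajectories from Day 1 of cohorts defined by their eventual transfusions.

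The cost is one revised definition and one relabelled table. Transfusion and sample dates are already collected, and SAP 9.3.3 already has a rule for partial transfusion dates.

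The drawback is small early groups. From 375 × [1 − exp(−L(t))], about 13, 25, 48 and 90 subjects per arm have been transfused by Weeks 13, 25, 49 and 97 at constant hazard, or 30, 40, 58 and 91 with the early threefold hazard. With independent events the 'more than one' group is nearly empty at Week 13. A sample drawn days after a transfusion would count as exposed, so some dilution remains.
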